### **6.9 Week 12:**

Patients with **bilobar disease** will undergo a contrast enhanced MR or CT, IR clinical office visit and response assessment. At the clinical office visit - compliance with HCQ therapy, toxicity and AEs will be recorded.

Patients with **unilobar disease** that **did not** undergo a **second session of TACE** will have an IR clinical phone call where compliance with HCQ therapy, toxicity and AEs will be recorded.

Patients with **unilobar disease** that **did** undergo a **second session of TACE** will not have any required study procedures at this time point.

CONFIDENTIAL

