Following TACE of the contra-lateral lobe, the patient will undergo repeat CBC, CMP and PT/INR at Week 10 to evaluate for dose limiting hepatotoxicity and nephrotoxicity. At Week 12, the patient will be evaluated with a clinical office visit, and contrast enhanced MRI or CT to assess imaging response of combined therapy. Patients will then undergo follow-up with clinical office visit, laboratory studies and imaging at 3 months (+/- 1 week) and 6 months (+/- 1 week) as part of routine clinical practice following TACE(41). Post-treatment imaging of all enrolled patients will be reviewed by a radiologist from the Abramson Cancer Center Clinical Imaging Core blinded to dose of HCQ. Post-treatment imaging will be assessed for mRECIST and EASL response to therapy and percentage of residual viable tumor. Response to therapy and progression of disease will be categorized using previously published mRECIST and EASL criteria (see Imaging Assessment of Response under Section 3.3)(42,43). These imaging criteria take into account percent necrosis as estimated by absence of tumor enhancement in addition to size reduction, and have been shown to correlate well with histopathologic data(13,44).

Follow-up study period to examine for late toxicity will end 6 months after cessation of HCQ therapy.

CONFIDENTIAL

This material is the property of the University of Pennsylvania. Do not disclose or use except as authorized in writing by the study sponsor

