**Timeline Unilobar HCC**

For patients with unilobar HCC, duration of HCQ therapy, frequency/timing of laboratory assessments, and definition of DLTs will be the same as with bilobar HCC. However, imaging, response assessment to initial TACE and phone call or clinical office visit following initial TACE will be performed at calendar Week 7. Repeat chemo-embolization may be performed at calendar Week 8 on HCCs with less than PR by mRECIST (see Imaging Assessment of Response under Section 3.3) or new HCCs which have developed since the initial TACE so long as LFTs are below the threshold of dose limiting toxicity. Subsequent follow-up clinic visits and imaging will be the same as with bilobar HCC - 3 months (+/- 1 week) and 6 months (+/- 1 week) following the last clinic visit.

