**Phase I: Dose Escalation using “3+3” Cohort Expansion Design**

After initiating HCQ, dose limiting toxicity will be defined as events occurring at any time from initiation of HCQ (Week 0) up to Week 12. All patients who receive at least one day of HCQ will be included in the toxicity analysis.

DLT definition:

Toxicities will be graded according to the Common Terminology Criteria of Adverse Events (CTCAE) version 4.0. A DLT will be defined as one or more of the following occurring any time during the defined DLT period from initiation of HCQ (i.e Day -42 to -28) to completion of HCQ therapy 4 weeks following second TACE (Day 56 to Day 63): (1) grade 3 or higher hepatobiliary complication, except hepatic pain; (2) grade 4 or higher hepatic pain; (3) grade 3 or higher abnormality of liver function tests including total bilirubin (i.e. >3x the upper limit of normal) and transaminases (i.e. >5x the upper limit of normal, the Hospital of the University of Pennsylvania defines normal transaminases as AST< 41 IU/L and ALT < 63 IU/L); (4) grade 3 or higher elevation of serum creatinine (i.e >3x baseline or >3x upper limit of normal); (5) grade 3 or higher increase in international normalized ratio (i.e. greater than 2.5x upper limit of normal or >2.5x baseline if anti-coagulated); or (6) any grade 3 or higher toxicity that is possibly or definitely related to treatment. Given the prevalence of baseline thrombocytopenia in patients with HCC, decreases in platelet count will not be evaluated as a DLT.

The initial dose of HCQ will be 400mg PO daily. If the initial dose of HCQ 400mg PO daily incurs DLT, the dose will be reduced to 200mg and an additional 3 patients will be enrolled at this level (see “3+3” Cohort Expansion chart below). If DLTs do not occur at HCQ 400mg PO daily, the dose will be escalated by 400mg increments to a maximally administered dose of HCQ 1200mg (administered as 600mg PO twice daily) with enrollment of each cohort dictated by the “3+3” design (see “3+3” Cohort Expansion and Dose Schema Charts below). The dose may be escalated to the next level once at least 3 patients at a particular HCQ dosage have been observed for 1 month after second TACE (i.e. day 56 to day 63).

“3+3” Cohort Expansion Design Decision Making Regarding Dose Escalation

“3+3” Cohort Expansion Design Decision Making Regarding Dose Escalation	
Number of Patients with DLT at a Given Dose Level	Escalation Decision Rule
0 out of 3	Escalate

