### **6.7 Week 8:**

Patients with **bilobar disease** will undergo TACE of the contra-lateral lobe to treat additional HCC. This second session of TACE will be performed only if the patient's clinical status and laboratory assessments have returned to baseline and the patient has not had any dose limiting toxicity.

Patients with **unilobar disease** will undergo an IR clinical office visit. At the clinical office visit - compliance with HCQ therapy, toxicity and AEs will be recorded. In order to determine if a second session of TACE is needed for subjects, a response assessment with imaging (contrast enhanced MRI or CT) will also be conducted at this visit.

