### **6.8 Week 10:**

Patients with **bilobar disease** and patients with **unilobar disease not undergoing a second session of TACE** will have laboratory assessments (CBC, PT/INR, CMP) to check for DLT.

Other patients with **unilobar disease** will undergo second session of TACE. This second session of TACE will be performed only if 1.) the HCC is less than PR by mRECIST or new HCC has developed since the initial TACE, 2.) the patient's clinical status and laboratory assessments have returned to baseline and 3.) the patient has not had any dose limiting toxicity.

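### In the readable text, bilobar and single-TACE unilobar patients have no scheduled blood draw in the nominal last 14 days of the DLT window, so a silent laboratory DLT could be missed before escalation

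*Combined protocol and SAP*

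**What the plan says.** **DLT window and escalation.** Sections 3.1 and 3.2 both run the DLT window from the start of HCQ to Week 12. Section 3.1 also gives the end in days, as Day 56 to Day 63. Escalation needs at least three patients at a dose who "have been observed for 1 month after second TACE (i.e. day 56 to day 63". Under Section 8.6 the medical monitor must review patient records for DLT before the dose goes up.

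**Laboratory criteria.** DLT criteria (3), (4) and (5) are numeric thresholds for bilirubin and transaminases, creatinine, and INR.

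**Scheduled bloods.** Sections 6.2 and 6.5 give all patients a panel at Weeks 2 and 6. At Week 10, Section 6.8 says that bilobar patients and unilobar patients without a second TACE "will have laboratory assessments (CBC, PT/INR, CMP) to check for DLT".

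**Week 12.** In Section 6.9 a bilobar patient "will undergo a contrast enhanced MR or CT, IR clinical office visit and response assessment". Single-TACE unilobar patients "will have an IR clinical phone call where compliance with HCQ therapy, toxicity and AEs will be recorded". Section 6.10 requires nothing of these two groups at Week 14.

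**Section 3.1 agrees.** Timeline Bilobar HCC puts the last panel at Week 10, then says: "At Week 12, the patient will be evaluated with a clinical office visit, and contrast enhanced MRI or CT". For unilobar patients, Timeline Unilobar HCC says that "duration of HCQ therapy, frequency/timing of laboratory assessments, and definition of DLTs will be the same as with bilobar HCC".

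**Next bloods.** Section 6.11 places them at the visit 3 months after HCQ stops. Timeline Unilobar HCC instead counts follow-up as "3 months (+/- 1 week) and 6 months (+/- 1 week) following the last clinic visit".

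**The concern.** A value over a bilirubin, transaminase, creatinine or INR threshold need not cause symptoms, so these criteria are reliably assessed only if blood is taken. An abnormality that starts between Weeks 2 and 6, or between Weeks 6 and 10, and persists can still be found by the next draw inside the window. One that starts after Week 10 has no later scheduled draw until escalation is already allowed. The monitor's record review cannot find a value that was never measured.

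A miss can only lower the DLT count, and under the 3+3 table a single event matters. At one DLT in three patients the plan adds three more at the same dose; at none in three it escalates. At two in six it stops; at one in six it can go on or declare the MTD.

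The plan itself treats this risk as central. Section 8.3.4 makes hepatic and renal toxicity after first TACE events of special interest, because that is when the two treatments are first combined. Section 1.4 reports no published human study of HCQ in HCC and no trial under way of HCQ with TACE.

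**Working it through.** **Inputs.** First TACE at Week 4 (Section 6.4), taken as Day 0. HCQ starts at Week 0. Second TACE for bilobar patients at Week 8 (Section 6.7). Last panel at Week 10 (Section 6.8). Window end at Week 12, or Day 56 to 63 (Section 3.1). Visit grace of 14 days and at most 15 weeks of HCQ (Section 6).

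**Formula.** Day = (Week − 4) × 7.

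**The plan's own figure.** Week 12 gives (12 − 4) × 7 = Day 56. Second TACE at Week 8 is Day 28, and 28 + 28 = Day 56. Both match the stated start of the Day 56 to 63 range.

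**Nominal gap.** Week 10 is Day 42, so the gap is 56 − 42 = 14 days.

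| Measured against | Calculation | Share |
|---|---|---|
| DLT window, Day −28 to Day 56 | 14/84 | 17% |
| Longest stated window, Day −42 to Day 63 | 14/105 | 13% |
| Month after second TACE (bilobar), Day 28 to 56 | 14/28 | 50% |
| Time after the only TACE (unilobar), Day 0 to 56 | 14/56 | 25% |

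These rows are one 14-day gap against four denominators, not four separate problems.

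**How timing moves the gap.**
- Week 10 draw taken 14 days late, on Day 56, with the window ending that day: 56 − 56 = 0 days.
- Second TACE on Day 35, window end on Day 63, draw moving with it to Day 49: 63 − 49 = 14 days.
- Same, but with the draw left at Day 42: 63 − 42 = 21 days.
- HCQ run to the 15-week cap (Week 15 = Day 77), draw on Day 42, and the window read as lasting as long as HCQ: 77 − 42 = 35 days. This is the extreme case and depends on that reading.

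**Next scheduled bloods** (taking 3 months as 13 weeks).
- Section 6.11: Week 12 + 13 = Week 25, which is 15 weeks after the Week 10 draw (14 to 16 with the ±1 week).
- Single-TACE patients, counting from the last clinic visit: that visit is at Week 7 in Section 3.1, giving Week 20, a gap of 10 weeks (9 to 11). It is at Week 8 in Section 6.7, giving Week 21, a gap of 11 weeks (10 to 12).

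On every reading the next bloods come after the window has closed.

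**The case against.** **The schedule may be in the missing figures.** The bilobar and unilobar timelines in Section 3.1 are figures that cannot be read here, and a Week 12 draw could appear there. A reader might infer that the plan contains no Week 12 bloods at all; that is not established. This stands as a caveat. It does not answer the point, because Sections 3.1 and 6.9 agree in writing, and the plan names bloods where it wants them, as at Week 10 and in Section 6.11.

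**The draws are placed sensibly.** They fall two weeks after HCQ starts and two weeks after each bilobar TACE. Section 1.1 says that in most studies liver tests return to normal within a week of TACE. Section 1.5 reports no hepatic toxicity in the HCQ cancer combinations. Single-TACE patients are sampled two and six weeks after their only procedure, so for them the case is weaker. Any intermittent schedule also leaves gaps. All of this lowers the expected number of late events. It does not supply a sample for the end of a window that the plan chose to run to Week 12, in a combination with no earlier trial.

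**Other safeguards exist.** A reader might infer that a silent DLT after Week 10 is bound to go uncounted. The documents do not support that. Toxicity is asked about at Week 12, Section 8.2 requires questioning and, where appropriate, examination at each contact, and unscheduled tests are not barred. An event is missed only if all of these fail to reveal it.

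**Conclusion.** The point holds as a gap in measuring the Phase I primary endpoint. For bilobar and single-TACE unilobar patients, the readable text has no scheduled sample for DLT criteria (3) to (5) in the nominal last 14 days before escalation is allowed. A laboratory DLT starting then could be missed, and any miss favours escalation.

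It would go too far to conclude that the MTD will be set too high, or by how much. The documents give no rate of late silent laboratory events, so no effect on the probability of escalation can be calculated.

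The verdict assumes that the unseen figures add no Week 12 draw and that visits run at their nominal weeks. The grace period can reduce the gap to zero, but nothing requires that, and it can also widen it. Unilobar patients with a second TACE are outside this point, except where the fix touches their schedule.

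**What to change.** 1. Add the existing CBC, CMP and PT/INR panel to the bilobar Week 12 visit, in Section 6.9 and in Timeline Bilobar HCC (Section 3.1). The nominal gap falls from 14 days to 0. These patients already attend for imaging.
2. In Section 8.6, require that result before the medical monitor's escalation review.
3. Preferably, add a blood draw with the Week 12 call for single-TACE unilobar patients. The downside is an extra laboratory visit.
4. State in Timeline Unilobar HCC which unilobar patients the Week 12 draw covers. That section copies the bilobar blood schedule without exception, while Section 6.9 requires nothing at Week 12 of unilobar patients who had a second TACE. Without this step, the change would create a new conflict for them.

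If the timeline figures already show a Week 12 draw, bringing the text into line with them and adding step 2 is enough.

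The cost is a schedule amendment, one routine draw per patient and a short wait for the result before escalation. The sample also gives an end-of-HCQ liver value, which helps the secondary objective on liver test abnormalities after Day 56. This is a cheap improvement.

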## **6 Study Procedures**

*Please Note - All visits will be by calendar week. All visits from Weeks 0 to 14 will have a grace period of 14 days/2 weeks to allow for scheduling of procedures, weekends, holidays as well as off service days for the interventionalist while not exceeding a total of 15 weeks total time taking HCQ. In addition, all study visits/events are sequential so that a patient cannot proceed to a study visit without completing the prior visit (e.g. Week 2 visit events must be completed before the Week 3 visit, Weeks 3 visit events must be completed before Week 4 visit, etc.).*

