### **6.6 Week 7:**

All patients will be contacted by phone after receiving the laboratory results to verify compliance with HCQ therapy and discuss toxicity and AEs.

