### **6.10 Week 14:**

Patients with **unilobar disease** that **did undergo** a **second session of TACE** will undergo a contrast enhanced MR or CT, IR clinical office visit and response assessment. At the clinical office visit - compliance with HCQ therapy, toxicity and AEs will be recorded.

Patients with **bilobar disease** and patients with **unilobar disease that did not undergo a second session of TACE** will not have any required study procedures at this time point.

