### **6.11 Follow-Up Q3 Months:**

Study follow-up of patients will occur at 3 months (+/- 1 week) and 6 months (+/- 1 week) after cessation of HCQ therapy (Week 12 or Week 14). The 3 month and 6 month follow-up visits will include contrast enhanced MRI or CT, laboratory assessments (CBC, PT/INR, CMP) and IR clinical office visits by an interventional radiologist. The follow-up study period will end at 6 months (+/- 1 week) after cessation of HCQ therapy (Week 12) to examine for late toxicity. Patients will continue to be followed beyond the end of follow-up study period per normal Interventional Radiology standard of care and *only* patient data regarding tumor progression and survival will be recorded during this time period to better assess LPFS and overall survival.

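### Unilobar patients given a second TACE: Sections 3.1 and 6 disagree on its week, and Section 6 lists no laboratory tests after it within the DLT window

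*Combined protocol and SAP*

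**What the plan says.** **Section 3.1.** Under the unilobar timeline, response imaging is at Week 7. A repeat TACE may follow at Week 8 for tumours with a response below PR or for new tumours. Laboratory timing and the DLT definition are carried over from bilobar disease. The bilobar text has blood tests at Week 6, two weeks after the first TACE, and at Week 10, two weeks after the second.

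**Section 6.** The visits differ:

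- Week 7 (6.6) is a telephone contact: "All patients will be contacted by phone after receiving the laboratory results to verify compliance with HCQ therapy".
- Week 8 (6.7), unilobar patients: "a response assessment with imaging (contrast enhanced MRI or CT) will also be conducted at this visit".
- Week 10 (6.8): bilobar patients and unilobar patients not retreated "will have laboratory assessments (CBC, PT/INR, CMP) to check for DLT". The remaining unilobar patients "will undergo second session of TACE. This second session of TACE will be performed only if" three conditions are met.
- Week 12 (6.9): retreated unilobar patients "will not have any required study procedures at this time point".
- Week 14 (6.10): imaging, an office visit and a response assessment. "At the clinical office visit - compliance with HCQ therapy, toxicity and AEs will be recorded". No blood tests are listed.
- Follow-up (6.11): the next listed tests are at visits timed "3 months (+/- 1 week) and 6 months (+/- 1 week) after cessation of HCQ therapy (Week 12 or Week 14").

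**DLT window.** Sections 3.1 and 3.2 close it four weeks, or one month, after the second TACE. Section 3.1 labels that point Day 56 to 63 and elsewhere gives Week 12; Section 3.2 labels it Week 12. Section 3.1 allows escalation once at least three patients have been observed for one month after the second TACE, with the same day label.

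**The concern.** DLT and MTD are the Phase I primary endpoints. Three of the six DLT criteria (liver tests, creatinine, INR) are laboratory values and cannot be established without a blood sample. Section 8.3.4 treats hepatic and renal toxicity after TACE as events of special interest.

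Section 3.1 counts every patient with at least one day of HCQ in the toxicity analysis. A retreated unilobar patient therefore enters the 3+3 count even if no blood is drawn after the second TACE, and could be recorded as free of laboratory DLT for want of a test. The dose chosen in Phase I is then given to as many as 46 − 6 = 40 further patients in Phase II.

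**Working it through.** **1. The plan's own label.** The initial TACE is at Week 4 (Section 6.4). Taking that as Day 0, Day = 7 × (Week − 4). Section 3.1 puts the second TACE at Week 8, which is Day 28. Day 28 + 28 = Day 56 = Week 12. The stated window end is reproduced.

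**2. The same rule under Section 6.** The second TACE is at Week 10, which is Day 42. Day 42 + 28 = Day 70 = Week 14. On this nominal schedule the labels close the window 70 − 63 = 7 to 70 − 56 = 14 days early, leaving 14 to 21 days of observation after that TACE instead of 28.

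**3. Listed laboratory sets between baseline and the 3-month visit.**

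| Group | Last TACE | Lab weeks | Sets after last TACE, in window |
|---|---|---|---|
| Bilobar (Section 6) | Week 8 | 2, 6, 10 | 1 |
| Unilobar, one TACE (Section 6) | Week 4 | 2, 6, 10 | 2 |
| Unilobar, two TACEs (Section 6) | Week 10 | 2, 6 | 0 |
| Unilobar, two TACEs (Section 3.1) | Week 8 | 2, 6, 10 | 1 |

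The zero is the same whether the window closes at Week 12, Day 63 or Week 14.

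**4. Next listed tests for the retreated group.** Take 3 months as 13 weeks.

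- HCQ stopped at Week 12: Week 25, which is 25 − 10 = 15 weeks after the second TACE.
- HCQ stopped at Week 14: Week 27, which is 27 − 10 = 17 weeks after it.
- With the one-week allowance the range is 14 to 18 weeks. Measured from Week 14, the tests come 11 to 13 weeks after the window has closed.

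**5. Effect of one uncounted DLT in the 3+3 table.**

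- 1 of 3 (add three patients) becomes 0 of 3 (escalate).
- 2 of 3 (stop) becomes 1 of 3 (add three patients).
- 2 of 6, reached as 1 + 1 (stop), becomes 1 of 6 (proceed or, at the highest tolerable dose, declare the MTD).

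Each change points towards a higher dose.

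**6. Illustration with assumed values.** The documents give neither the DLT rate nor the share that would be missed. Let p be the true DLT rate at a dose, m the share of all DLTs at that dose left uncounted, and q = p(1 − m). The chance of escalating from that dose is (1 − q)³ + 3q(1 − q)⁵.

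| p | m = 0 | m = 10% | m = 25% |
|---|---|---|---|
| 0.20 | 0.709 | 0.752 | 0.814 |
| 0.33 | 0.434 | 0.500 | 0.605 |
| 0.50 | 0.172 | 0.234 | 0.351 |

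These figures show sensitivity only. They do not estimate the effect in this trial.

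**The case against.** The strongest reply is that the gap rests on the silence of one section. Section 3.1 says that unilobar laboratory timing matches bilobar timing, which suggests a draw after the second TACE was intended. The timeline charts are not in the text available for review and may show one. This stands as a limit: a reader might infer that the plan deliberately leaves these patients untested, and the documents do not support that. But a Week 10 draw carried over from Section 3.1 would coincide with a Week 10 TACE, not follow it.

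Other safeguards help only in part:

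- The allowance "All visits from Weeks 0 to 14 will have a grace period of 14 days/2 weeks" can move a visit but adds no blood test.
- The requirement in Section 6.8 that laboratory values be back at baseline is a check before the TACE.
- Results from the overnight stay are of little use here, because Section 3.2 excludes the day immediately after TACE from DLT assessment.
- The medical monitor (Section 8.6) can review only tests that were drawn.
- Unscheduled tests may be done, and clinically evident DLTs can be recorded at Week 14.

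A reader might also infer that the end of the DLT window is irreconcilable for this group. That goes too far. Section 5.2 puts the end of HCQ at roughly Week 12, but the Study Summary allows 12 to 15 weeks of administration, Section 6 caps it at 15 weeks, Section 6.10 records HCQ compliance at Week 14, and Section 6.11 names Week 14 as a possible stop. All of these fit a Week 14 end, so the fault lies in labels that were not updated. The 7 to 14 day shortfall also assumes that HCQ starts at Day −28. With the Day −42 start that Section 3.1 permits, Week 10 is Day 28 and the day labels fit.

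Finally, a reader might see a conflict with the Section 2 objective on late liver-test abnormalities after Day 56. The Day 56 to 63 label already overlaps that period for every patient, and Section 3.3 counts late toxicity at any point in therapy or follow-up, so one event may belong to both endpoints.

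**Conclusion.** The two sections conflict on the week of the unilobar response imaging and second TACE. Followed as written, Section 6 leaves retreated unilobar patients, and no other group, without a listed test of the three laboratory DLT criteria between the last TACE and the end of the window. The gap to the next listed set is about 15 to 17 weeks on the nominal schedule.

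Any resulting error in the MTD is upward. Its size is unknown, because the documents give neither the share of unilobar patients retreated nor the rate of laboratory DLTs. It would arise only where a retreated Phase I patient has a laboratory DLT that is clinically silent and not caught by an unscheduled test. The point should be fixed because it touches the Phase I primary endpoint and patient safety. The outdated window labels are secondary.

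**What to change.** 1. State one week for the unilobar response imaging and one for the second TACE, identically in Sections 3.1 and 6.
2. Schedule CBC, CMP and PT/INR two weeks after the second TACE in this group (Week 12 if TACE is at Week 10), matching the interval used after the other sessions.
3. Define the end of the DLT window and of escalation observation by events alone: the later of 8 weeks after the initial TACE and 4 weeks after the last TACE. Drop the fixed Week 12 and Day 56 to 63 labels. On the nominal schedule this gives max(12, 12) = Week 12 for bilobar patients, max(12, 8) = Week 12 for unilobar patients with one TACE, and max(12, 14) = Week 14 for a second TACE at Week 10. It also covers patients who never have a second TACE, for whom the current event wording gives no end date.
4. Require the post-TACE results before a patient is counted DLT-free for escalation.

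The cost is amendment wording, one routine blood draw per retreated unilobar patient, and up to about two weeks' delay to an escalation decision when a cohort includes such a patient.
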